**Study 111-301 Statistical Analysis Plan****4.6.3 Interim Analysis**

No formal interim futility/efficacy analyses are planned for this study.

An independent DMC is acting as an advisory body to BioMarin and provides input on the safety data collected in the study. The safety outputs are generated by an external party with an external independent statistician. DMC data review occurs approximately every **CBI** during the study (or ad hoc, if necessary).

**Study 111-301 Statistical Analysis Plan****5 GENERAL ANALYSIS CONSIDERATIONS**

The analyses described in this SAP are based on Amendment 4 of the protocol (dated 01-February-2019).

Individual subject data that is reflected in data summaries will be provided in **PI**. Unless otherwise specified, all **PI** will be by treatment group and ordered by subject number, where subject number includes the site number.

Summary tables and figures are provided by treatment group with no overall population column. There are certain exceptions (e.g. subject disposition, demographics, baseline characteristics and safety data) which are indicated in the relevant sections.

Baseline annualized growth velocity (AGV) is defined in Section 14.3.1. Baseline growth measures (other than AGV) and baseline weight are those assessed on Day 1 of dosing, regardless of timing relative to dosing. (Note: If no assessments are available, then the baseline assessment will be the last non-missing assessment prior to Day 1). All other baseline assessments are the last non-missing on-study 301 assessments prior to administration of study drug. Change from baseline is calculated as: [post-baseline value – baseline value]; Percent change from baseline is calculated as: ([post-baseline value – baseline value]/baseline value) x 100.

The Screening visit will not be presented in descriptive summaries over time. When the analysis windows have been applied (see Section 5.4), data collected at the screening visit may be included in the Baseline assessment. All assessments will be listed, but only those assessments assigned to visits according to the windows applied (see Section 5.4) will be summarized in tables or graphically. Exceptions to this are summaries of the worst post-baseline laboratory data in shift tables where all assessments are considered, and also the standing height assessments displayed in the spaghetti plots.

Unless otherwise specified, the number of subjects, mean, 25th percentile, median, 75th percentile and estimates of precision (e.g. SD, confidence interval) will be displayed to one more decimal place than the collected data. Minimum and maximum values will be presented to the same decimal places as the collected data. For summaries by visit, the number of subjects with non-missing observations (n) according to the analysis windows (see Section 5.4 for further details) at the derived visit will be presented.

When summarizing categorical data, for mutually exclusive categories, the sum of the individual categories, including a separate “Missing” category, should equal 100%. Unless otherwise specified, if categories have no data, then they will not be displayed.

Study 111-301 Statistical Analysis Plan

All statistical analyses will be performed using SAS® version 9.4 or a later release (SAS Institute, North Carolina, USA) and results be presented in the form of tables, **PI** and graphs (TLGs). All statistical analyses, including dataset creation and output generation, will be performed by Biostatistics and Statistical Programming personnel of BioMarin's Biometrics department.

5.1 Analysis Populations

A total of 5 analysis populations will be used for all summaries and analyses. Subjects who have satisfied the population criteria will be classified in the designated population and analyzed accordingly.

The analysis populations are described below. For each population, the number and percent of subjects included, excluded, and the reason for exclusion (where applicable) will be summarized by treatment group and overall. **PI** will be provided to identify any subjects not included in the population, and the reason for exclusion.

The number of subjects in the Full Analysis Set (FAS) will also be summarized by randomization strata (i.e., Male Tanner Stage I, Female Tanner Stage I, Male Tanner Stage >I, Female Tanner Stage >I).

5.1.1 Full Analysis Set

The Full Analysis Set (FAS) is defined according to the intention-to-treat principle and includes all randomized subjects with a signed informed consent. The FAS will be used to present the baseline characteristics, and efficacy data by randomized treatment group. All listings, excluding screen failures, will be produced on the FAS.

5.1.2 Per-Protocol

The Per-Protocol (PP) population will be determined consistent with the International Conference on Harmonisation (ICH) E9 Guideline (http://www.emea.europa.eu/docs/en_GB/document_library/Scientific_guideline/2009/09/WC500002928.pdf) and is defined as a subset of the FAS population who are compliant with the protocol.

The PP population will comprise of all subjects in the FAS who satisfy the following criteria:

- 1) Subjects who met all inclusion/exclusion criteria.
- 2) Subjects who had no major protocol deviations that could affect the results of the primary or key secondary endpoints (AGV, height Z-score, and upper to lower body segment ratio).**

**Study 111-301 Statistical Analysis Plan**

- 3) Subjects who were assigned into the correct strata.
- 4) Subjects who completed the treatment originally allocated (i.e., always received the assigned treatment (BMN 111 or placebo), had a Week 52 visit within the defined visit window (see Section 5.4), and were at least 90% compliant with study drug).

Subjects who always received the assigned treatment (4) can only be determined once the study has been unblinded.

**The major protocol deviations that would exclude a subject from the PP population are:

- Evidence of taking growth hormone (coded as “somatropin and somatropin agonists”) or gonadotropin-releasing hormone (coded as “gonadotropin releasing hormone analogues”)
- Evidence of having a limb lengthening procedure (i.e., a MedDRA preferred term of ‘limb operation’).

The PP population will be used for the analysis of the primary and two key secondary endpoints.

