BioMarin, regulatory agencies, and the IRB/IEC/REB. It is the investigator's (or designee's) responsibility to obtain written permission to use protected health information per country-specific regulations, such as the Health Insurance Portability and Accountability Act of 1996 (HIPAA) in the USA, from each subject (or the subject's legally authorized representative). If permission to use protected health information is withdrawn by the subject, it is the responsibility of the investigator to obtain a written request from the subject to ensure that no further data will be collected from the subject. The subject will then be removed from the study.

It is a priority of the study to maximize study subject retention and adherence to study-specific procedures. The completeness of the study data may affect the integrity and accuracy of the study results. Therefore, subjects who discontinue study treatment should be encouraged to continue to undergo as many of the protocol-specified procedures and assessments as possible for the remainder of the study, as long as such continued participation does not detrimentally affect the health, safety, or welfare of the subject and consent remains in place. It is important that following treatment discontinuation the original visit schedule is strictly adhered to.

For subjects who discontinue BMN 111 or placebo but remain in the study, PK and BMN 111 activity assessments will be waived completely; vital signs and clinical labs/biomarkers will be obtained only once at each visit subsequent to BMN 111 or placebo discontinuation. Pre-and post-dose designations will not apply as the subject has discontinued dosing and vital sign and clinical lab/biomarkers assessments previously designated as "post-dose" will be waived. All other assessments at each visit should be completed if possible and the subject is willing. Data from the study procedures and assessments may be used to further characterize the natural progression of ACH.

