12 COMPLIANCE

Treatment compliance will be calculated based on the study drug preparation and study drug administration records captured in the eCRF, and summarized by treatment group for the safety population.

For each daily injection, the amount of study drug taken will be calculated as the number of units in the syringe pre-injection, minus the number of units remaining in the syringe post-injection. If the number of units in the syringe pre-injection is not captured in the eCRF, then it will be assumed to be the same as the planned dose.

The total amount of study drug taken will be calculated as the amount of study drug taken (units) in the corresponding treatment duration.

The total amount of study drug planned is determined based on the duration of treatment, and the planned units per day.

Percentage compliance for each subject will be derived from the total amount of study drug intake divided by the planned study drug intake, and multiplied by 100:

$$\text{Treatment Compliance (\%)} = \frac{\text{Total Amount of Study Drug Taken (units)}}{\text{Total Amount of Study Drug Planned (units)}} \times 100$$

Treatment compliance will be calculated and summarized by treatment group.

- Compliance with protocol-specified treatment regimen (%)
- Compliance with protocol-specified treatment regimen ($\geq 50\%$, $\geq 60\%$, $\geq 70\%$, $\geq 80\%$, $\geq 90\%$, $\geq 100\%$)

Study 111-301 Statistical Analysis Plan

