13 EXTENT OF EXPOSURE TO STUDY DRUG

Dosing information is recorded by subjects (in the paper diary) and also by the site on visit days. In the case of duplicate records with the same date, if the investigator confirms the date, then investigator reported dosing data will be used. All summaries will be based on the safety population, and presented by treatment group.

The day of the first dose of study drug is referred to as Day 1. A missed dose is defined as a calendar day without a dose between the date of Day 1 and date of last dose.

Descriptive statistics will be provided for the following variables:

- Duration of treatment (days)
 - = Date of last dose – Date of first dose + 1
- Total number of doses administered
 - = Number of doses administered between date of Day 1 and date of last dose
- Total number of doses missed
 - = Number of doses missed between date of Day 1 and date of last dose
- Total amount of weight adjusted dose administered (ug/kg)
- Average weight-adjusted daily dose administered (ug/kg/day)

The frequency and percent of subjects will be provided for the following variables, where missed doses are counted between the date of first dose (Day 1) and date of last dose:

- Number of subjects who missed at least one dose
- Number of subjects who missed more than one dose
- Number of subjects who missed more than 5 consecutive doses
- Number of subjects who missed more than 10 consecutive doses

The frequency and percent of all missed doses will be provided for the following variable:

- Reason for missed dose (Site Error, Parent/Caregiver Error, Home Health Error, Adverse Event, Other, Missing).

PI

**Study 111-301 Statistical Analysis Plan****14 EFFICACY EVALUATIONS****14.1 General Approaches for Analyzing Growth Parameters**

All growth parameters assessed by anthropometric measurements are measured at Day 1, Week 13, Week 26, Week 39 and Week 52.

Growth parameters are measured 3 times for each assessment. It is the mean of these 3 assessments that are considered for the summaries and analyses. In the event that all 3 are not available, the mean of the 2, or the individual assessment is taken.

All efficacy endpoints will be assessed using the FAS. In addition, the primary and key secondary endpoints (AGV, height Z-score, and upper to lower body segment ratio) will also be assessed using the PP population.

Estimand formulations are provided for the primary and key secondary endpoints.

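### Read as written, the Per-Protocol compliance test stops at each child's last dose, so a child who stops drug early but attends Week 52 can enter the Per-Protocol set

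*SAP*

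**What the plan says.** SAP Section 5.1.2 sets four criteria for the PP set. The fourth opens "Subjects who completed the treatment originally allocated (i.e., always received the assigned treatment (BMN 111 or placebo" and continues with the other two tests: "had a Week 52 visit within the defined visit window (see Section 5.4), and were at least 90% compliant with study drug". The SAP adds: "Subjects who always received the assigned treatment (4) can only be determined once the study has been unblinded".

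Section 12 defines compliance as units taken divided by units planned, times 100. For the denominator: "The total amount of study drug planned is determined based on the duration of treatment, and the planned units per day". For the numerator: "The total amount of study drug taken will be calculated as the amount of study drug taken (units) in the corresponding treatment duration".

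Section 13 gives duration of treatment as "Date of last dose – Date of first dose + 1". It counts missed doses over the same span: "A missed dose is defined as a calendar day without a dose between the date of Day 1 and date of last dose".

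Protocol Section 9.3.4 says that "subjects who discontinue study treatment should be encouraged to continue to undergo as many of the protocol-specified procedures", and that they should keep to the original visit schedule. SAP Section 4.2 repeats the encouragement to stay. A child who is off drug can therefore have a Week 52 visit in the Day 344 to 386 window.

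The PP set is used to repeat the analyses of annualized growth velocity (AGV), height Z-score and upper:lower body segment ratio.

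**The concern.** A PP analysis is meant to show the result in children who followed the assigned regimen, here daily injections for 52 weeks. If compliance is measured only while a child is still dosing, stopping early costs nothing in the score. The Week 52 visit test does not close the gap, because it records attendance and not dosing. The two major deviations listed as excluding a child from PP are growth hormone or gonadotropin-releasing hormone use and limb lengthening; neither covers early stopping.

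What is at stake is how the supportive analysis reads. Children who were off drug for a large part of the year would pull the PP estimates towards the FAS result, and the FAS already uses off-treatment heights by design (SAP Sections 14.1 and 14.3.2). Agreement between the two would then say less than it appears to.

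**Working it through.** **The plan's own figure.** The inputs are 55 per arm, a difference of 1.75 cm/yr, SD 2.80 and two-sided alpha 0.05 (SAP Section 4.5). The standard error of the difference is 2.80 × √(2/55) = 0.534, and 1.75/0.534 = 3.28. Power is 0.906 by the normal approximation and 0.901 by the noncentral t with 108 degrees of freedom. The stated 90% or so is reproduced. The point does not depend on it, but the 1.75 and the standard error are used below.

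**Compliance under the two denominators.** Assume constant planned units per day and no missed dose until the child stops on day *d*.

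- SAP Sections 12 and 13: *d*/*d* = 100%, whatever *d* is.
- Planned course of 52 × 7 = 364 days: *d*/364.

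| Last dose | SAP as written | Of 364 days |
|---|---|---|
| Day 92 | 100% | 25.3% |
| Day 120 | 100% | 33.0% |
| Day 183 | 100% | 50.3% |
| Day 274 | 100% | 75.3% |
| Day 327 | 100% | 89.8% |
| Day 328 | 100% | 90.1% |

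Over 364 days, such a child fails the 90% test if the last dose falls before Day 328. As written, the child never fails it.

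**The three tests for a child who stops on Day 120 and attends Week 52.**

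1. Assigned product: met, because the child never received the other arm's product.
2. Week 52 visit in window: met.
3. At least 90% compliant: met, at 100%.

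If criteria 1 to 3 of the PP definition are also satisfied, the child is in the PP set.

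**Dilution of the PP difference in AGV.** The documents do not say how many children stop drug and stay in follow-up, so the counts are assumed. Suppose *k* of 55 BMN 111 children in the PP set stopped at Week 13, and that the 1.75 cm/yr effect accrues in proportion to time on drug. Each then loses 1 − 13/52 = 0.75 of the effect, and the dilution is (*k*/55) × 0.75 × 1.75:

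- *k* = 2: 0.05 cm/yr
- *k* = 5: 0.12 cm/yr
- *k* = 8: 0.19 cm/yr

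Against the standard error of 0.534, this is about 0.09 to 0.36 of one standard error. Later stopping gives less.

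**The case against.** The strongest reply is that criterion 4 begins by requiring completion of the allocated treatment. SAP Sections 6 and 7 treat completing study drug and completing the study as separate statuses, so a child who stops on Day 120 is a discontinuer in the SAP's own disposition tables. Section 5.1.2 also describes the PP set as compliant with the protocol. This shows what was probably intended. It does not settle the rule, because the opening phrase is immediately spelled out by the three tests and none of them requires dosing to Week 52. The word *always* does not supply the requirement either. The SAP says that this element can be determined only after unblinding, which fits receipt of the correct arm's product; stopping drug is visible while blinded.

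Second, Section 12 does not refer to Section 13, and the protocol gives the duration of treatment as 52 weeks. A 52-week denominator is therefore a possible reading. However, Section 12 counts drug taken over the corresponding treatment duration, which points to the child's own period, and Section 13 holds the only formula in the SAP. If 52 weeks was meant, the text still has to say so.

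Third, a reader might infer that the compliance table hides early stopping. The documents do not support that. Completion of treatment (Section 6), reasons for stopping study drug (Section 7), duration of treatment in days (Section 13) and adverse events leading to discontinuation (Section 15.1.1) are all reported by treatment group.

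Fourth, the consequence is modest. The PP analyses are non-confirmatory repeats. If the drug works, dilution makes the PP result less favourable to it, so this route does not manufacture a finding of efficacy. That stands.

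**Conclusion.** The point holds as a gap between the apparent intent of criterion 4 and the tests that define it. On the most natural reading of Sections 5.1.2, 12 and 13, a child who stops drug early without missed doses and attends Week 52 scores 100% and enters the PP set. The text is ambiguous enough that a programmer could decide otherwise, which is itself a reason to settle it.

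The effect is a possible dilution of the supportive PP estimates of AGV, height Z-score and upper:lower ratio towards the FAS result. For AGV it is about 0.05 to 0.19 cm/yr. That range rests on 2 to 8 of 55 BMN 111 children stopping at Week 13 and meeting the other PP criteria, and on an effect that accrues evenly with time on drug. The counts are assumptions, and the true number could be zero. No corresponding size is worked out for the two key secondary endpoints.

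A reader might also infer that the trial's main conclusion is at risk. It is not: the FAS primary analysis, the control of type I error and the power do not use the PP set.

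**What to change.** Amend criterion 4 in SAP Section 5.1.2 before unblinding. For PP membership, calculate compliance with planned units from Day 1 to the Week 52 visit, count every day after the last dose as not taken, and keep the SAP's 90% threshold. For a visit on Day 365, a child who stops on Day 120 then scores 120/365 = 33% and is excluded. With no missed doses, the earliest last dose that passes is Day 310 for a visit on Day 344 (310/344 = 90.1%) and Day 348 for a visit on Day 386 (348/386 = 90.2%).

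A simpler alternative is to add to criterion 4 that study drug was continued to the Week 52 window.

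The cost is one sentence and one denominator, and the PP set may lose a few children. Making the change before unblinding matters because part of criterion 4 is assessed only afterwards, and membership should not then turn on interpretation. A second row in the Section 12 table, showing compliance against the full 52-week regimen, is optional.

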5.1.3 Safety

The Safety Population is defined as all subjects in the FAS who receive at least one dose of double-blind BMN 111 or placebo in this study.

The Safety Population will be used to present the safety summaries by actual treatment received. Subjects randomized to one treatment group, who only receive the study drug for the other treatment group, will be analyzed in the arm of the study drug they received.

5.1.4 PK

The PK Population is defined as all subjects in the FAS randomized to the BMN 111 treatment group, who receive at least one dose of BMN 111 in this study and have at least one evaluable PK concentration.

5.1.5 Immunogenicity

The Immunogenicity Population is defined as all subjects in the Safety Population who have at least one evaluable immunogenicity sample. Subjects randomized to one treatment group, who only receive the study drug for the other treatment group, will be analyzed in the arm of the study drug they received.

5.2 Pooling of Data from Sites with Small Enrollment

Not applicable, as there are no analyses by site.

Study 111-301 Statistical Analysis Plan

5.3 Study Day Derivation

Study day in 111-301 will be determined by subtracting the initial study drug start date from a visit date plus 1 if the visit date occurs on or after the initial study drug start date. Otherwise, the study day will be the visit date minus the initial study drug start date. Therefore, Study Day 1 will occur on the initial study drug start date. i.e.

- Study Day 1 = Day of first dose of study drug.
- If Visit Date < Study Drug Start Date, then Study Day = (Visit Date - Study Drug Start Date)
- If Visit Date > Study Drug Start Date, then Study Day = (Visit Date - Study Drug Start Date) +1

5.4 Visit Windows for Analysis

An assessment for a subject will be classified according to the study day of the assessment where it falls within a window.

Data in Study 111-901 for subjects who enrolled in Study 111-301 and are included in the corresponding analysis population will be used in efficacy summary tables and figures. The analysis visits and windows for assessments in Study 111-901 are defined in Table 5.4.1. Unless otherwise specified, only the derived visits listed in the table will be included in summary tables and figures.

Table 5.4.1: Visit Windows for Observed Assessments in BMN 111-901

Derived Visit	Target Day ^a	Analysis Window ^a
≥ 6 Months Prior	-182	> -364 to ≤ -182
≥ 12 Months Prior	-364	> -546 to ≤ -364

^a Target days and analysis windows are relative to the 111-301 Day 1 date defined in Section 5.3 above.

For each subject and growth measure in Study 111-901, the record closest to the target day within the analysis window will be retained for inclusion in summary tables.

Spaghetti plots of standing height and standing height Z-scores will include all measures recorded in Study 111-901 up to and including the “≥ 12 Months Prior” assessment without applying windows. This will allow for all subjects with height assessments ≥ 12 months prior to Day 1 to have at least one assessment included.

The analysis windows for assessments in Study 111-301 are defined in [Table 5.4.2](#). The analysis windows are designated for each scheduled visit and centered on a target day. If

	Study 111-301 Statistical Analysis Plan
---	--

there are two or more assessments within a designated window, the assessment that is closest to the target day will be used for analyses. If the two closest assessments to the target day are equidistant from the target day, the assessments taken on a scheduled visit per CRF page will be used. Unless otherwise specified, all analyses are based on derived visits.

Table 5.4.2: Visit Windows for Observed Assessments in 111-301

Derived Visit	Target Day ^a	Analysis Window ^a
Baseline		The last assessment prior to the first dose of study drug unless otherwise specified.
Day 1	Day 1	Day 1
Day 2	Day 2	Day 2
Day 3	Day 3	Day 3
Day 10	Day 10	Day 4 – 16 (-/+6)
Week 6	Day 43	Day 22 - 64 (-/+21)
Week 13	Day 92	Day 71 – 113 (-/+21)
Week 26	Day 183	Day 162 - 204 (-/+21)
Week 39	Day 274	Day 253 – 295 (-/+21)
Week 52	Day 365	Day 344 – 386 (-/+21)

^a Target days and analysis windows are relative to the 111-301 Day 1 date defined in Section 5.3.

